6.3.1 Time Period and Frequency for Collecting AE and SAE Information

All AEs and SAEs will be collected from randomization until the end of the study at the timepoints specified in the SoA.

All SAEs will be recorded and reported to the Sponsor or designee within 24 hours, as indicated in Appendix 2. The Investigator will submit any updated SAE data to the Sponsor within 24 hours of it being available.

Investigators are not obligated to actively seek AEs or SAEs after the conclusion of study participation. However, if the Investigator learns of any SAE, including a death, at any time after a participant has been discharged from the study, and he/she considers the event to be reasonably related to the study or study participation, the Investigator must promptly notify the Sponsor.

The method of recording, evaluating, and assessing causality of AEs and SAEs and the procedures for completing and transmitting SAE reports are provided in Appendix 2.

Care will be taken not to introduce bias when detecting AEs and/or SAEs. Open-ended and non-leading verbal questioning of the participant is the preferred method to inquire about AE occurrence.

6.3.2 Follow-up of AEs and SAEs

Ongoing AEs and SAEs will be followed until resolution or stability as determined by the Investigator.

6.3.3 Regulatory Reporting Requirements for SAEs

Prompt notification (within 24 hours, see Appendix 2) by the Investigator to the Sponsor of an SAE is essential so that legal obligations and ethical responsibilities towards the safety of participants and the safety of a study treatment under clinical investigation are met.

The Sponsor has a legal responsibility to notify both the local regulatory authority and other regulatory agencies about the safety of a study treatment under clinical investigation. The Sponsor will comply with country-specific regulatory requirements relating to safety reporting to the regulatory authority and IRB.

Investigator safety reports must be prepared for suspected unexpected serious adverse reactions (SUSAR) according to local regulatory requirements and Sponsor policy and forwarded to Investigators as necessary.

7 Statistical Considerations

7.1 Sample Size Determination

Sample sizes are estimated to achieve 80% power based on a 1-sided 5% significance level. As this is an exploratory proof of concept trial, a 1-sided 5% significance level was selected. The within subject standard deviation is assumed to be 1 hour and the minimum treatment difference is assumed to be 0.5 hours.

When there are 2 treatments and a sample size of 14 in each of the 2 sequences, a 2x2 Williams Crossover Design will have approximately 82% power to detect a minimum pairwise difference of 0.5 or greater, assuming that the standard deviation of the paired differences is 1 at a one-sided 5% significance level.

Assuming ~20% dropout and total of 36 patients (18/sequence) is planned.

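### Section 7.1 sets both the within-subject SD and the SD of the paired differences to 1 hour; both cannot hold, and under the first the power is about 57%, not 82%

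*Protocol*

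**What the plan says.** Section 7.1 (Sample Size Determination) of the protocol sets the target: "Sample sizes are estimated to achieve 80% power based on a 1-sided 5% significance level". Its first paragraph then gives the variability and the effect: "The within subject standard deviation is assumed to be 1 hour and the minimum treatment difference is assumed to be 0.5 hours".

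The second paragraph turns to the design, 14 participants in each of two sequences, and puts the power for a 0.5-hour difference at about 82%. That figure is given on a condition about variability that differs from the one in the first paragraph: "assuming that the standard deviation of the paired differences is 1 at a one-sided 5% significance level". The section closes with an allowance of about 20% for dropout, which leads to 36 patients.

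Two differently named SDs are therefore each set to 1 hour. No correlation or conversion factor links them, and no source is given for either.

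**The concern.** In the usual crossover model the within-subject SD is the residual SD of one participant's result in one period. The TPAP-minus-APAP difference for a participant contains two such residuals, so its variance is twice the within-subject variance. A within-subject SD of 1 hour and a paired-difference SD of 1 hour are two different assumptions, a factor of √2 apart.

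The SD drives the whole section. The 28 completers, the inflation to 36 and the claim of at least 80% power on the primary endpoint (nightly usage) all follow from it. If the within-subject figure is the real assumption, the trial has little better than an even chance of detecting its own target. A non-significant result would then say much less about the absence of a benefit than the stated power suggests.

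**Working it through.** **Inputs, all from section 7.1.** One-sided α = 0.05; difference δ = 0.5 h; N = 28 (14 per sequence); SD = 1 h, labelled once as within-subject and once as the SD of the paired differences; stated power about 82%; dropout about 20%; planned total 36.

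**Method.** Noncentral t for the treatment contrast in a 2x2 crossover with equal sequences:

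- standard error = SD_diff / √N
- noncentrality = δ / standard error
- degrees of freedom = N − 2 = 26, critical value t(0.95; 26) = 1.706
- power = P(T > 1.706), with T noncentral t on 26 df

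**Step 1: reproduce the protocol's figure (SD_diff = 1 h).**

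- Standard error = 1/√28 = 0.189 h
- Noncentrality = 0.5/0.189 = 2.646
- Power = 82.4%

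This matches the stated figure. A paired t test with 27 df gives 82.5% and the normal approximation 84.2%. A two-sided 5% test gives 72.1%, so the one-sided level was indeed used. The dropout step also reproduces: 28/(1 − 0.20) = 35, or 36 for equal sequences.

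**Step 2: convert between the two SDs.** SD_diff = √2 × SD_within.

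- SD_within = 1 h gives SD_diff = 1.414 h.
- SD_diff = 1 h gives SD_within = 1/√2 = 0.707 h.

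**Step 3: power under the first paragraph's assumption (SD_within = 1 h).**

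- Standard error = 1.414/√28 = 0.267 h
- Noncentrality = 0.5/0.267 = 1.871
- Power = 57.0% (57.1% with 27 df, 58.9% by the normal approximation)

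**Step 4: what each reading implies.**

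| | SD_diff = 1 h | SD_within = 1 h |
|---|---|---|
| Implied other SD | SD_within 0.71 h | SD_diff 1.41 h |
| Power at 28 completers, δ = 0.5 h | 82.4% | 57.0% |
| Smallest N for 80% power | 27 (28 with equal sequences) | 51 (52 with equal sequences) |
| Difference detectable with 80% power at N = 28 | 0.48 h | 0.68 h |

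The dropout allowance does not close the gap. If all 36 planned patients were evaluable, power under SD_within = 1 h would be 66.8%. Reaching 52 completers at 20% dropout would take 52/0.80 = 65 enrolled.

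**The case against.** The best defence is that this is loose wording. Both paragraphs use the same pair of numbers, 1 and 0.5, and the second names its SD precisely. The author of the first may simply have meant the SD of the within-subject differences. On that reading the power, the 28 completers and the inflation to 36 all stand, and only a label is wrong. The 82% is not miscalculated: it is tied expressly to the paired-difference SD and reproduces on that input. The trial also calls itself exploratory, and the correction changes no analysis, population or procedure.

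Much of this stands. The 82% is right for its own input, and the 57% is conditional on the other reading. But the text does not say that the first SD refers to differences, and with no source for either figure the label reading cannot be confirmed. A reader who takes the within-subject SD at its usual meaning and puts it into a standard crossover formula gets 57%. The exploratory status is offered as the reason for the one-sided 5% level; it does not reconcile two incompatible inputs.

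One caution applies to the planned total. Section 7.1 plans 36 patients, whereas the synopsis (section 1.1) states that 32 will be enrolled. The power figures at 28 completers do not depend on which of these is right.

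**Conclusion.** The section is wrong as written. Two SD assumptions for one calculation differ by a factor of √2, and nothing else in the protocol reconciles them. The stated 82% holds only if 1 hour is the SD of the paired differences. If 1 hour is the within-subject SD, power is about 25 percentage points lower and well short of the section's own 80% target.

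This rests on the usual meaning of within-subject SD (residual SD per period), equal sequences, 28 completers and a one-sided 5% t test. The choice between the t and normal calculations moves the results by about two points and does not affect the conclusion. Which SD was intended cannot be settled from the protocol.

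**What to change.** Keep one SD in section 7.1, name it exactly and state where it comes from.

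- If 1 hour is the SD of the paired differences, say so in the first paragraph and add that this corresponds to a within-subject SD of about 0.71 hour. The 82% and the 28 completers then stand.
- If 1 hour is the within-subject SD, give the paired-difference SD as 1.41 hours, restate power at 28 completers as about 57%, and give the difference detectable with 80% power as about 0.68 hour.

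The cost is a sentence or two. Neither correction requires a change in enrolment, though the second makes the stated power or detectable difference less favourable. Should the sponsor want 80% power for 0.5 hour under the second reading, that is a separate decision and would need about 52 completers.

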7.2 Randomization

The treatment arm is determined by random selection using an MS Excel spreadsheet on the night of the study. The spreadsheet generates a number between 1 and 10,000. The TPAP therapy will be the starting therapy when an even number is generated by the spreadsheet; the CPAP therapy will be the starting therapy when an odd number is generated.

7.3 Populations for Analyses

For the purposes of analysis, the following analysis sets are defined:

Set	Description
Randomized	All participants who were randomized.
Modified Intent to Treat (mITT) Set	The mITT set comprises all participants who are randomized, undergo at least 1 night in either study arm, and have at least 1 measurement on the primary endpoint. Participants will be analyzed for equivalence.
Safety Set	The Safety Set consists of all participants who are randomized and undergo at least 1 night in either study arm.
Per Protocol (PP) Set	The PP Population consists of all participants without any major protocol violations and have considered to be evaluable for study analysis.

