Within the TPAP arm, participants will be set to a double Comfort Setting drop according to the following table. This drop schedule will be implemented even while the TPAP device is operating with automatic pressure adjustment.

P _{set} (cmH ₂ O)	Pressure Drop 1 (cmH ₂ O)	Pressure Drop 2 (cmH ₂ O)
5.0 - 5.9	0	0
6.0 - 6.9	1	0
7.0 - 7.9	2	0
8.0 - 8.9	2	1
9.0 - 9.9	2	2
10.0 - 20.0	2	3

Table 1: Comfort Setting Pressure Drops 1 and 2 to be used at the specified target set pressure to the patient.

Participants will use their starting therapy nightly at home for 6 weeks after which time they will undergo a washout period of 1 week where no therapy will be used. Following the washout period, they will initiate another 6-week usage with the second therapy. Afterward, they will return to the office to receive their permanent equipment. Phone calls as reminders to end the first arm, start the washout period, then to start the second arm will be made.

Immediately after both arms of the study are completed, the following will occur:

- Eligibility criteria will be reviewed and confirmed
- Participants will be asked to respond to the following
 - ESS (Epworth Sleepiness Scale)
 - FOSQ (Functional Outcomes of Sleep Questionnaire)

During the home use period, subjects will be called at the following time points during each arm of the study. At each time point, adverse events and compliance with the device will be assessed. Subjects using the device less than an average of 5 hours per night during the first week will be contacted on a more regular basis (weekly until 5 hour per night use is achieved) to address any problems and encourage use. If patients discontinue use of the device during the home use period, they will still be encouraged to return for all testing per protocol. If a patient refuses to come in for further testing, they will be considered a lost to follow up and excluded from efficacy analysis.

- 1 Day Phone Call (+2 days)
- 7 Day Phone Call (+/- 3 days)
- 14 Day Phone Call (+/- 3 days) IF deemed necessary per 7 Day compliance
- 28 Day Phone Call (+/- 3 days) Check-in

- Week 6 Phone Call (+/- 3 days) – End first arm, fill out questionnaires, start Washout Period
- Week 7 Phone Call (+/- 3 days) - Review protocol, start 2nd arm
- Week 12 (+/- 3 days) - Equipment Return

Data collected from the therapy device will include the following:

- Usage averaged over the 6-week period and nightly
- Leak averaged over the 6-week period and nightly

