2.2.3 Biological Rationale

TPAP is an innovative device/algorithm designed to deliver a lower inspiratory than expiratory PAP. The drop in inspiratory pressure can be modulated during the inspiratory phase. Previous research has shown that reducing inspiratory PAP by placing a resistor in the inspiratory line can enhance subjective comfort and decrease leaks when compared to CPAP, despite maintaining a similar residual apnea-hypopnea index (AHI). However, the resistor could only provide a fixed inspiratory PAP reduction based on existing PAP settings. TPAP addresses this limitation by allowing for adjustable drops in inspiratory PAP throughout the inspiration phase, offering a potentially more personalized and adaptive therapeutic approach.

3 Endpoints

	Endpoints
Primary	
• Nightly adherence (usage) with device (TPAP versus APAP)
Secondary	
• Evaluation of P95, Leak and AHI over each 6-week period• 6-week Subjective Questionnaires (TheraPAP versus APAP) following each arm
◦ ESS◦ FOSQ• Adverse Event rate
Safety Endpoints²	
• Spontaneous adverse events

² Although there will not be any direct treatment vs. control comparison here, we will assume that CPAP is safe and that any abnormal value recorded in the next morning compared to the evening before the polysomnography is due to treatment with TPAP.

4 Study Design

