4.1 Overall Design

Safety issues regarding this study are detailed in Appendix 1: Regulatory, Ethical, and Study Oversight Considerations.

The TheraPAP Adherence 1 Study is a randomized, controlled, crossover study in PAP-naïve participants with OSA. Pre-screening is conducted to establish potential eligibility based on an in-lab polysomnogram (PSG), a PSG split-night PSG/titration or a home sleep study (HST) that has been conducted within the previous 3 months. Participants would then be recruited as described below. For those who consent, they will be given the equipment and instructions to complete both arms of the study but will have their therapy device set to the parameters necessary to start the first arm, which will be randomly assigned. They will use the device nightly for 6 weeks, after which they will use no therapy for 1 full week (washout period). During this washout period, their therapy device will be remotely set to their second arm. When they restart therapy, they will use the device nightly for a further 6 weeks. During each arm, various data will be remotely collected from their therapy device, and after completion of each arm, they will fill out 3 questionnaires and average data during the 6 weeks of that arm will be downloaded. Once all activities are completed, they will be eligible to receive the incentive pay and their involvement will be completed.

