5.9 Participant Discontinuation/Withdrawal from the Study

A participant may withdraw from the study at any time at his/her own request or may be withdrawn at any time at the discretion of the Investigator for safety, behavioral, or administrative reasons.

If the participant withdraws consent, the Sponsor may retain and continue to use any data collected before such a withdrawal of consent.

All participants who withdraw from the study with an ongoing AE must be followed until the event is resolved or deemed stable.

Participation may be terminated before completing the study and the reason recorded as follows:

- Withdrawal due to AE
- Participant withdrew consent at their own request, (e.g., intolerance to study procedures)
- At the discretion of the Investigator for safety, behavioral, or administrative reasons
- Other reasons, as they occur

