Records and documents, including signed ICF, pertaining to the conduct of this study must be retained by the Investigator for 5 years after study completion unless local regulations or institutional policies require a longer retention period. No records may be destroyed during the retention period without the written approval of the Sponsor. No records may be transferred to another location or party without written notification to the Sponsor.

All data generated by the site personnel will be captured and stored in an internal password-protected system.

6 Source Documents

Source documents provide evidence for the existence of the participant and substantiate the integrity of the data collected. Source documents are filed at the site.

7 Publication Policy

The Sponsor will generally support publication, reserving the right to review prior to submission.

Authorship will be determined by mutual agreement and in line with the International Committee of Medical Journal Editors' authorship requirements.

A summary of the study results will also be posted in a publicly accessible database (e.g., www.ClinTrials.gov).

8 Protocol Approval and Amendment

Before the start of the study, the study protocol and/or other relevant documents will be approved by the IRB/Competent Authorities, in accordance with local legal requirements. The Sponsor must ensure that all ethical and legal requirements have been met before the first participant is enrolled in the study.

This protocol is to be followed exactly. To alter the protocol, amendments must be written, receive approval from the appropriate personnel, and receive IRB/Competent Authority approval prior to implementation (if appropriate). Any deviations from the protocol will be reported to the Sponsor as Protocol Deviations.

Administrative changes (not affecting the participant benefit/risk ratio) may be made without the need for a formal amendment. All amendments will be distributed to all protocol recipients, with appropriate instructions.

9 Liability and Insurance

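### The mITT set requires a night on the device, which is itself the primary outcome, so a randomised participant who never uses it is dropped instead of counted at 0 h

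*Protocol*

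**What the plan says.** Section 3 (Endpoints) gives the primary endpoint as "Nightly adherence (usage) with device (TPAP versus APAP"). Section 7.3 defines the mITT set as randomised participants who "undergo at least 1 night in either study arm, and have at least 1 measurement on the primary endpoint".

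Three other places bear on how that rule works:

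- Section 4.2.1: the starting arm is assigned at the office visit, and the device is then set up and handed over. Randomisation therefore precedes any night at home.
- Sections 4.2.2 and 6.1: usage is collected remotely each day, and 4.2.2 names the primary analysis as one purpose.
- Section 1.1: the trial is open label.

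The protocol does not say whether a night at home with no use counts as a night in an arm, or as a measurement of the endpoint.

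**The concern.** In a drug trial, requiring one dose before a participant enters the efficacy set is a condition on exposure. Here the same kind of rule is a condition on the outcome, because a night on the device is what the primary endpoint measures. Someone randomised and issued the device who never uses it has the worst possible result, 0 h in each arm. That result can be known from the daily remote data. Leaving such people out selects on the outcome. Average use in both arms then looks better than it was among those randomised, and any true difference between TPAP and APAP is scaled up. The rule stands in the protocol itself, so it is not a detail left for a later document.

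**Working it through.** **Inputs from the protocol (7.1).** Design difference 0.5 h; SD of paired differences 1 h; one-sided 5% test; 14 per sequence (28) evaluable; about 20% dropout; 36 planned.

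**The plan's own figures.** The noncentrality is 0.5/(1/√28) = 2.65. With 26 degrees of freedom, the noncentral t gives 82.4% power, against the stated 82% or so. Dropout: 28/0.8 = 35, against 36 planned. Both reproduce, so 0.5 h, 1 h and 36 serve as reference values below.

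**Assumed.** The protocol gives no rate of never-use, so k, the number of never-users among 36, is taken as 1 to 3. Period effects are ignored.

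**Step 1: who leaves.** The rule asks for one night in either arm, so anyone with a single night in one arm stays. Only people with no night in both arms leave. Each of them has a paired difference of 0 - 0 = 0.

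**Step 2: the estimate.** Let D be the mean difference among the 36-k starters.

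- All randomised: D × (36-k)/36.
- mITT as worded: D.
- Ratio: 36/(36-k).

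The same ratio applies to mean use in each arm, because a never-user adds 0 h to both.

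**Step 3: the test.** Let starters have mean 0.50 h and SD 1 h, with m = 36-k.

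- Starters only: t = 0.50 × √m.
- With k zeros added: sum of squares = (m-1) × 1² + m × 0.50² - 36 × (mean of all)²; SD = √(sum of squares/35); t = mean of all × 6/SD.

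For k = 3, the mean of all is 16.5/36 = 0.458. The sum of squares is 32 + 8.25 - 7.56 = 32.69, the SD is 0.966, and t = 0.458 × 6/0.966 = 2.85.

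| k | 36/(36-k) | Difference, starters (h) | Difference, all randomised (h) | t, starters | t, all randomised |
|---|---|---|---|---|---|
| 1 | 1.029 | 0.50 | 0.49 | 2.96 | 2.95 |
| 2 | 1.059 | 0.50 | 0.47 | 2.92 | 2.90 |
| 3 | 1.091 | 0.50 | 0.46 | 2.87 | 2.85 |

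Even with six never-users the factor is 36/30 = 1.20.

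**Step 4: no true difference.** If the mean over all randomised is 0, the starters' mean is 0 × 36/(36-k) = 0. Dropping never-users cannot produce an effect.

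**Step 5: the other sample size.** The Synopsis (1.1) gives 32 participants, not 36. With 32 the factors are 32/31 = 1.032, 32/30 = 1.067 and 32/29 = 1.103, which leaves the conclusion unchanged.

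**The case against.** The best defence is that the wording may not drop anyone. It speaks of undergoing a night, not of using the device. If the remote system returns 0 h for an idle night, a never-user has a measurement and could qualify. That reading is possible, but nothing in the protocol states it, and the natural reading goes the other way. The second defence is size: one night in either arm is enough to stay in, and the arithmetic shows a modest inflation with almost no change in the test. That stands, and it limits the weight of the point.

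A reader might infer three stronger things, none of which the protocol supports.

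- **That low users fall out of the per-protocol set.** The argument would run from nightly use as an instruction (4.1), through "This protocol is to be followed exactly" (Appendix 1), to a set made up of "all participants without any major protocol violations and have considered to be evaluable for study analysis". But only major violations exclude. Appendix 1 says deviations are reported to the sponsor; it does not grade them or tie them to an analysis set. Sections 1.1 and 4.2.2 answer low use with extra calls. What counts as major or evaluable is commonly settled in the statistical analysis plan, which is not shown. Any figure for the resulting bias would need a usage cut-off that the protocol does not contain.
- **That low users can be withdrawn by the investigator.** Section 5.9 says a participant "may be withdrawn at any time at the discretion of the Investigator for safety, behavioral, or administrative reasons". It does not mention device use, and withdrawal after one measured night would not remove anyone from the mITT set.
- **That every night without recorded use should be 0 h.** This goes too far. Someone with, say, 4 h a night in period 1 (assumed) who withdraws before period 2 would be scored as a 4 h difference, eight times the 0.5 h design difference, on a therapy never tried. Lost transmissions would also be scored as non-use.

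Separately, 1.1 and 4.2.2 say of patients who refuse further testing or surveys that "they will be considered a lost to follow up and excluded from efficacy analysis" (wording of 1.1). That rule fits poorly with 7.3 and should be reconciled with it, but the present point does not rest on it.

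**Conclusion.** The point holds in a narrow form. As naturally read, the mITT rule removes randomised never-users although device use is the primary outcome and their value is an observed 0 h. Mean use in both arms and the TPAP-APAP difference are overstated by 36/(36-k): about 3% to 9% for 1 to 3 never-users. The test is almost unaffected, and no false difference can arise by this route. The size rests on an assumed count of never-users, on starters at 0.50 h with SD 1 h, and on no period effect. The reason to change the text is that the selection is on the outcome and removing it costs almost nothing; the likely bias is not large.

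**What to change.** In 7.3:

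1. Define the mITT set as all randomised participants who were issued the device.
2. State that a participant who remains in the study but does not use the device has a primary-endpoint value of 0 h for those nights.
3. State that nights after withdrawal from the study, a second period never started because of withdrawal, and data-transmission failures are treated as missing and not as 0 h.

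The cost is a few sentences, plus a working rule for telling an unused night from a failed transmission. The downside is that mean use in both arms and the estimated difference become slightly less favourable.

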2.1 Study Rationale

A device able to provide inspiratory positive airway pressure (PAP) < expiratory PAP, designated TPAP, is being developed by SleepRes for the treatment of obstructive sleep apnea (OSA). In prior studies, the administration of higher inspiratory than expiratory PAP did not substantially increase treatment efficacy or adherence to continuous PAP (CPAP), which remains low. In our recent investigation, we demonstrated that the addition of a resistor to the CPAP circuit to reduce inspiratory PAP increased subjective comfort. The present study, TheraPAP Adherence, is a Crossover study designed to examine whether TPAP can improve adherence over CPAP as an at home treatment for OSA.

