4.2.2 First 6-Week Arm

Patients will start using their equipment the first night. The study coordinator will monitor usage nightly and after the third night with a minimum of 5 hours of use, they will remotely adjust the device pressure range to P95 ± 2 cmH₂O, using the P95 from the third night. This range will be used for the remainder of both arms of the study. During the study, daily remote collection of usage will be conducted both for later primary endpoint analysis and to guide further contact with the patient if they need help.

During usage in the first arm, P95 and AHI will be monitored to assure that the patient is receiving proper therapy. If P95 is near the upper limit and the AHI is above 5 events per hour, the range will be bumped up by 2 cmH₂O.

A contact schedule will also be set up with each patient to follow up on any needs for help. Similar interaction is customary with new CPAP patients. The schedule is as follows and will be conducted on both arms of the study:

- 1 Day Phone Call (+2 days)
- 7 Day Phone Call (+/- 3 days)
- 14 Day Phone Call (+/- 3 days) IF deemed necessary per 7 Day compliance
- 28 Day Phone Call (+/- 3 days)

Participants using the device less than an average of 5 hours per night during the first week will be contacted on a more regular basis (weekly until 5 hour per night use is achieved) to address any problems and encourage use. If patients discontinue use of the device during the home use period, they will still be encouraged to complete surveys per protocol. If a patient refuses to complete such surveys, they will be considered lost to follow up and excluded from efficacy analysis.

At the end of the 6-week period, patients will stop using any sleep therapy for 1 week as a washout between arms. The study coordinator will remotely switch the mode of operation of the

therapy device to that for the second arm employing the same pressure range as was used in the bulk of the first arm. Patients will be asked to fill out the questionnaires during this period (ESS and FOSQ). Additionally, the following data averaged over the 6-week period of the trial will be downloaded from the device:

- Usage
- Leak
- P95
- AHI

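### Section 7.3 assigns the mITT set an equivalence analysis, but the trial's aim and its power statement are about showing a difference in favour of TPAP

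*Protocol*

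**What the plan says.** Protocol Section 7.3 lists the analysis sets. The mITT row defines membership (randomised, at least one night in either arm, at least one measurement of the primary endpoint) and then adds: "Participants will be analyzed for equivalence". The sentence names no endpoint, margin or procedure. It is the only mention of equivalence in the protocol, and the only sentence in Section 7 that says what kind of analysis a set receives.

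Three other places describe the comparison differently:

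- Section 2.1 says the study is "designed to examine whether TPAP can improve adherence over CPAP as an at home treatment for OSA".
- The Synopsis (Section 1.1) says it examines the difference in adherence between the treatments.
- Section 7.1 gives 14 participants per sequence "approximately 82% power to detect a minimum pairwise difference of 0.5 or greater". That figure takes the paired differences to have an SD of 1 and tests one-sided at 5%.

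Section 3 names nightly usage, TPAP versus APAP, as the primary endpoint.

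**The concern.** A superiority or difference test puts no difference under the null hypothesis and tries to reject it. An equivalence test puts a difference at least as large as a margin under the null and tries to reject that. For one endpoint and one comparison these are opposite claims. The mITT set is defined by having a primary-endpoint measurement, so the natural reading is that the sentence concerns nightly usage, the outcome named in the study aim and the natural subject of the 0.5 h power statement in Section 7.1.

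An equivalence analysis of usage would not answer whether TPAP improves adherence. With a narrow margin it would usually declare nothing when the planned benefit is present. With a wide margin it would call that benefit equivalence. Anyone writing or checking the analysis from this protocol has two incompatible statements of the main inference to work from.

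**Working it through.** **Inputs from Section 7.1.** One-sided 5% level; difference 0.5 h; 14 per sequence, so n = 28 completers; SD of paired differences 1 h. Degrees of freedom for a 2×2 crossover: 28 − 2 = 26.

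**Step 1: the plan's own figure.**

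- Standard error = SD/√n = 1/√28 = 0.189 h.
- Noncentrality = 0.5/0.189 = 2.646.
- Critical value t(0.95; 26) = 1.706.
- Power = P(noncentral t with 26 df and noncentrality 2.646 exceeds 1.706) = 82.4%.

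This agrees with the stated figure of about 82%, so the sample size is consistent with a one-sided test of no difference.

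**Step 2: does the 82% rule out equivalence?** No. One-sided 5% is also the per-side level of the two one-sided tests (TOST) procedure. TOST power depends mainly on the distance from the true difference to the nearer margin. A 1.0 h margin with a true difference of 0.5 h leaves 1.0 − 0.5 = 0.5 h. A 0.75 h margin with a true difference of 0.25 h also leaves 0.5 h. Both give 82.4% with 28 completers. The numbers alone do not separate the two kinds of test; the wording of Sections 2.1 and 7.1 does.

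**Step 3: what following the sentence would do.** The protocol gives no margin, so 0.5 h and 1.0 h are assumed. Equivalence is declared when the two-sided 90% interval lies wholly inside ± margin. The probabilities come from integrating over the chi-square distribution of the variance estimate with 26 df; a simulation of 2,000,000 draws agrees.

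Section 7.1 also describes the 1 h differently: "The within subject standard deviation is assumed to be 1 hour". On that reading the SD of a paired difference is √2 × 1 = 1.41 h, the standard error is 1.41/√28 = 0.267 h and the noncentrality is 0.5/0.267 = 1.87. Both readings are shown.

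| True benefit 0.5 h, n = 28, 5% per side | SD of differences 1 h | SD of differences 1.41 h |
|---|---|---|
| One-sided difference test succeeds | 82.4% | 57.0% |
| Equivalence declared, margin 0.5 h (assumed) | 5.0% | 3.2% |
| Equivalence declared, margin 1.0 h (assumed) | 82.4% | 57.0% |

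With the 0.5 h margin the true benefit sits on the boundary, so TOST rejects at no more than its 5% level. With the 1.0 h margin, equivalence would be declared as often as the difference test would succeed, and the same benefit would be reported with the opposite label.

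**The case against.** The strongest reply is that this is a stray sentence. It sits in a table cell that defines who belongs to a set, it names no endpoint or margin, and no equivalence test could be run from it alone. It may be a slip for a rule about how mITT participants are handled, such as analysis as randomised. The aim and the power statement both point the other way, the trial calls itself exploratory, and the realistic harm is confusion rather than a wrong conclusion. On this view the margin calculations measure nothing in the plan, because the margins are assumed.

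Much of this is fair. The sentence may well be a slip, and the percentages above are illustrations that carry no part of the contradiction. It is also true that Section 7.1 neither uses the word superiority nor states a direction; the direction is inferred from Section 2.1 together with the one-sided level.

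The conclusion still stands. The protocol does not say that the sentence is a slip, and Appendix 1 requires the protocol to be followed exactly. Nor is this a matter of detail properly left to the statistical analysis plan. The point is not that a margin or model is missing. It is that the protocol affirmatively states an analysis that conflicts with its own aim.

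**Conclusion.** The concern holds. Section 7.3 states an inference that contradicts the aim in Section 2.1 and the power wording in Section 7.1, and no other section reconciles them. The conclusion rests on the wording and on reading the mITT sentence as referring to the primary endpoint. It does not depend on any assumed margin or on which reading of the 1 h SD is right. The sample size is unaffected: 28 completers give 82.4% for the one-sided difference test with an SD of paired differences of 1 h. The correction should be made, but the point is moderate in weight, because the intended aim can be inferred from the rest of the document.

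**What to change.** - Delete the equivalence sentence from the mITT row of Section 7.3.
- State once, in Section 7.1 or in a short primary-analysis paragraph, that the primary comparison of nightly usage is a one-sided 5% test of superiority of TPAP over APAP.
- If the sentence was meant as a rule for handling mITT participants, write that rule in its place. If equivalence was meant for another endpoint, name that endpoint in a separate sentence.

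This edit should not be used to settle which analysis set is primary. Section 7.3 names none, and Sections 1.1 and 4.2.2 each remove some participants by their own rule ("they will be considered a lost to follow up and excluded from efficacy analysis" and "they will be considered lost to follow up and excluded from efficacy analysis"). That needs a separate decision.

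The cost is one sentence removed and one added, with no change to sample size or conduct.
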